### 8.1 Definitions

#### Unanticipated Problems Involving Risk to Subjects or Others (UPIRTSO)

Any unanticipated problem or adverse event that meets the following three criteria:

- Serious: Serious problems or events that results in significant harm (which may be physical, psychological, financial, social, economic, or legal) or increased risk for the subject or others (including individuals who are not research subjects). These include: (1) death; (2) life threatening adverse experience; (3) hospitalization - inpatient, new, or prolonged; (4) disability/incapacity - persistent or significant; (5) birth defect/anomaly; (6) breach of confidentiality; and (7) other problems, events, or new information (*i.e.* publications, DSMB reports, interim findings, product labeling change) that in the opinion of the local investigator may adversely affect the rights, safety, or welfare of the subjects or others, or substantially compromise the research data, **AND**
- Unanticipated: (*i.e.*, unexpected) problems or events are those that are not already described as potential risks in the protocol, consent document, not listed in the Investigator's Brochure, or not part of an underlying disease. A problem or event is "unanticipated" when it was unforeseeable at the time of its occurrence. A problem or event is "unanticipated" when it occurs at an increased frequency or at an increased severity than expected, **AND**
- Related: A problem or event is "related" if it is possibly related to the research procedures.

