## **8.2 Recording of Adverse Events**

At each contact with the subject, the study team must seek information on adverse events by specific questioning and, as appropriate, by examination. Information on all adverse events should be recorded immediately in the source document, and also in the appropriate adverse event section of the case report form (CRF) or in a separate adverse event worksheet. All clearly related signs, symptoms, and abnormal diagnostic, laboratory, or procedure results should be recorded in the source document.

All adverse events occurring during the study period must be recorded. The clinical course of each event should be followed until resolution, stabilization, or until it has been ultimately determined that the study treatment or participation is not the probable cause. Serious adverse events that are still ongoing at the end of the study period must be followed up, to determine the final outcome. Any serious adverse event that occurs during the Adverse Event Reporting Period and is considered to be at least possibly related to the study treatment or study participation should be recorded and reported immediately.

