### 8.3.1 Sponsor-Investigator Reporting: Notifying the Mayo IRB

The sponsor-investigator will report to the Mayo IRB any UPIRTSOs and Non-UPIRTSOs according to the Mayo IRB Policy and Procedures.

Information collected on the adverse event worksheet (*and entered in the research database*):

- Subject's name
- The date the adverse event occurred
- Description of the adverse event
- Relationship of the adverse event to the research drug: Not Related, Possibly Related, Probably Related, or Related
- If the adverse event was expected
- The severity of the adverse event: (Mild, symptoms such as GI upset, nausea, or headache; Moderate, symptoms such as vomiting, vertigo, chest pain; Severe, any problem requiring more than one day of OTC medication, or requiring a doctor visit, such as chest pain, vertigo, GI bleeding, *etc*)
- If any intervention was necessary/action taken
- Resolution: was the incident resolved spontaneously or after discontinuing treatment
- Date of Resolution

The Investigator will review all adverse event reports to determine if specific reports need to be made to the IRB and FDA. The sponsor-investigator will sign and date the adverse event report when it is reviewed. For this protocol, only directly related SAEs/UPIRTSOs will be reported to the IRB. Non-UPIRTSOs/non-serious AEs will be reported at the time of annual continuing review, according to the IRB policy.

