### 8.6.1 Internal Data and Safety Monitoring Board

There will not be a formal DSMB. However, we will have a DSMP and the PI will monitor the progress of the study and all adverse events.

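### Section 8.3.1 restricts IRB reporting to directly related events, an undefined term narrower than the possibly related threshold in 8.1 and 8.2, so a serious, unanticipated, possibly related event can miss prompt IRB review

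*Combined protocol and SAP*

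**What the plan says.** Four places in the protocol bear on when an event goes to the IRB.

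- **Section 8.1, UPIRTSO definition.** An event must be serious, unanticipated and related. It counts as related "if it is possibly related to the research procedures".
- **Section 8.2.** An SAE in the reporting period that is "considered to be at least possibly related to the study treatment or study participation should be recorded and reported immediately". The recipient is not named.
- **Section 8.3.1.** The opening sentence reads: "The sponsor-investigator will report to the Mayo IRB any UPIRTSOs and Non-UPIRTSOs according to the Mayo IRB Policy and Procedures". After the list of worksheet items comes the restriction that, for this protocol, "only directly related SAEs/UPIRTSOs will be reported to the IRB". The next sentence adds: "Non-UPIRTSOs/non-serious AEs will be reported at the time of annual continuing review, according to the IRB policy".
- **Section 8.3.1, worksheet.** Causality is recorded as "Relationship of the adverse event to the research drug: Not Related, Possibly Related, Probably Related, or Related".

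On oversight, section 8.6.1 says "There will not be a formal DSMB" and gives the monitoring of adverse events to the PI. Section 8.5 leaves further action after a severe event to the direction of the FDA and the IRB.

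**The concern.** The protocol uses one relatedness threshold to decide what a UPIRTSO is and a narrower one to decide whether the IRB hears of it. The narrower one cannot be applied consistently, because nobody completing the worksheet is asked whether an event is *directly* related. Staff who followed the restrictive sentence to the letter would be following the protocol, yet could hold back an event that 8.1 classes as an unanticipated problem.

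What is at stake is independent safety oversight. With no formal DSMB, and with the PI monitoring all adverse events, the IRB is one of the few bodies outside the study team that could act on a signal. Section 8.5 relies on it to do so, and it cannot direct action on an event that it has not been told about. The trial also has no control arm, which makes a confident causal call on any single event harder.

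**Working it through.** No arithmetic applies: the point involves no rate, sample size or error probability, and the plan gives no figure to reproduce. The check sets the relatedness wording side by side and follows test cases through it.

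**Thresholds as written**

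| Place | Purpose | Relatedness required |
|---|---|---|
| 8.1 | Defines a UPIRTSO | Possibly related to research procedures |
| 8.2 | Immediate reporting of SAEs, recipient not named | At least possibly related to treatment or participation |
| 8.3.1, opening sentence | Reporting to the IRB under its policy | None beyond the UPIRTSO definition |
| 8.3.1, restrictive sentence | Reporting to the IRB for this protocol | Directly related, undefined |
| 8.3.1, worksheet | Records causality to the drug | Not, Possibly, Probably, Related |

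**Case A: serious, unanticipated, graded Possibly Related**

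1. Under 8.1 it meets all three elements (taking the worksheet grade as the relatedness call), so it is a UPIRTSO.
2. Under 8.2 it is to be reported immediately, to someone.
3. Under the opening sentence of 8.3.1 it goes to the IRB.
4. Under the restrictive sentence it does not, since possibly related is not directly related on any ordinary reading.
5. The annual-review sentence covers Non-UPIRTSOs and non-serious events. This event is a UPIRTSO and is serious, so that sentence does not reach it.

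Steps 3 and 4 conflict inside one section. If step 4 governs, step 5 leaves the event with no stated route to the IRB.

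**Case B: as A, but graded Probably Related**

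Steps 1, 2, 3 and 5 are unchanged. Step 4 cannot be settled, because the protocol does not say whether *directly* takes in Probably.

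**Case C: serious, anticipated, graded Possibly Related**

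This fails the unanticipated element of 8.1, so it is a Non-UPIRTSO, and the annual-review sentence covers it on its face. The gap is therefore confined to unanticipated events.

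**The case against.** The best case for the current text has three parts.

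**The event may still reach the IRB.** The opening sentence of 8.3.1 promises reporting of any UPIRTSO under IRB policy, and that policy may require it whatever the protocol says. The restrictive sentence can also be parsed as two items, directly related SAEs on the one hand and UPIRTSOs as defined in 8.1 on the other, in which case Case A is reported. This stands as far as the consequence goes. A reader might infer that such events will miss the IRB; the documents support only that they can, since the policy is not among them. It does not rescue the wording. A sentence that begins by limiting itself to this protocol and uses *only* reads most naturally as a study-specific restriction. If IRB policy requires more, the sentence conflicts with that policy and still needs correcting.

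**Other safeguards exist.** Section 8.3.2 sends unexpected serious suspected reactions to the FDA within 7 or 15 calendar days. Section 8.5 pauses the study for formal review after a severe event during dosing, stops study drug in any subject with an SAE, and sets a study-wide SAE limit. These are real and reduce what is at stake. None of them notifies the IRB.

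**Section 8.2 names no recipient.** Correct. It shows that the protocol treats possibly related as the trigger for immediate reporting of SAEs, but a reader who took it as creating a duty to the IRB would go further than the text.

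**Conclusion.** The point holds as an internal inconsistency: the restrictive sentence in 8.3.1 conflicts with the opening sentence of the same section, with the UPIRTSO definition in 8.1 and with the threshold in 8.2, and it rests on a term that the protocol neither defines nor records. Its reach is one class of event: serious, unanticipated, and graded Possibly (perhaps also Probably) Related. That such an event can miss prompt IRB review assumes that the restrictive sentence is read as governing and that IRB policy does not override it.

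Several larger claims are tempting and are not supported:

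- *That all serious, possibly related events lack a route.* Anticipated ones are Non-UPIRTSOs and fall under annual review.
- *That a countable share of the worksheet grades is excluded.* This would require *directly related* to mean the grade Related, which the protocol does not say.
- *That reports would be delayed until the annual review.* The annual-review sentence does not cover the event at all, so the documents imply no particular delay.
- *That most events needing review would be filtered out.* The documents give no SAE rate and no distribution of causality grades, and section 1.6 says that serious events are not expected.

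The matter should be corrected because it concerns safety oversight and is cheap to put right. It does not affect the primary analysis.

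**What to change.** In 8.3.1, replace the restrictive sentence with: *All UPIRTSOs as defined in 8.1 (serious, unanticipated and at least possibly related) will be reported promptly to the IRB according to IRB policy.* Keep the annual-review sentence for Non-UPIRTSOs and non-serious events. In 8.2, state to whom SAEs that are at least possibly related are reported immediately.

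The replacement should refer to UPIRTSOs and not to all possibly related SAEs. The broader wording would bring in anticipated SAEs and clash with the annual-review sentence that follows. When the amendment is drafted, note also that the worksheet grades relation to the drug, whereas 8.1 speaks of research procedures; the form should allow either to be recorded.

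The cost is one replacement sentence, a short addition to 8.2 and a small check of the worksheet, with perhaps a few more prompt IRB reports. No analysis or sample size changes.

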### 8.3.2 Sponsor-Investigator Reporting: Notifying the FDA

The sponsor-investigator will report to the FDA all unexpected, serious suspected adverse reactions according to the required IND Safety Reporting timelines, formats, and requirements.

Unexpected fatal or life threatening suspected adverse reactions, where there is evidence to suggest a causal relationship between the study drug and the adverse event, will be reported as a serious suspected adverse reaction. This will be reported to the FDA on FDA Form 3500A, **no later than 7 calendar days** after the sponsor-investigator's initial receipt of the information about the event.

Other unexpected serious suspected adverse reactions, where there is evidence to suggest a causal relationship between the study drug and the adverse event, will be reported as a serious suspected adverse reaction. This will be reported to the FDA on FDA Form 3500A, no later than 15 calendar days after the sponsor-investigator's initial receipt of the information about the event.

Any clinically important increase in the rate of serious suspected adverse reactions over those listed in the protocol or product insert will be reported as a serious suspected adverse reaction. This will be reported to the FDA on FDA Form 3500A **no later than 15 calendar days** after the sponsor-investigator's initial receipt of the information about the event.

The sponsor-investigator must also notify the FDA (and sponsors must notify all participating investigators) in an IND safety report of potential serious risks, from clinical trials or any other source, as soon as possible, but in **no case later than 15 calendar days** after the sponsor determines that the information qualifies for reporting under § 312.32(c)(1)(i)-(iv).

Findings from other studies in human or animals that suggest a significant risk in humans exposed to the drug will be reported. This will be reported to the FDA on FDA Form 3500A, **no later than 15 calendar days** after the sponsor-investigator's initial receipt of the information about the event.

## 8.4 Pregnancy

Pregnancy, in and of itself, is not regarded as an AE unless there is suspicion that the study drug may have interfered with the effectiveness of a contraceptive medication or method. When a pregnancy has been confirmed in a participant during maternal exposure to study drug, the following procedures should be followed in order to ensure safety:

- The study drug must be discontinued immediately.
- The investigator must complete and submit a Clinical Trial Pregnancy Form to the sponsor or its designee with 24 hours of learning of the pregnancy.

Pregnancy should be recorded on a Clinical Trial Pregnancy Form and reported by the investigator to the sponsor or its designee. Pregnancy follow-up information should be recorded on the same form and should include an assessment of the possible causal relationship to the sponsor's study drug to any pregnancy outcome, as well as follow-up to the first well-baby visit or the duration specified in local regulations, whichever is later.

**Any SAE occurring during pregnancy of a study participant must be recorded on the Serious Adverse Event Report Form and submitted to the sponsor or its designee.**

Abnormal pregnancy outcomes (eg, spontaneous abortion, fetal death, stillbirth, congenital anomalies, or ectopic pregnancy) are considered SAEs and must be reported.

## 8.5 Stopping Rules

All subjects will be assessed during the 2 cycles each lasting for 2 days of Fisetin administration (after Visits 1 and 2; total 4 days) and during each visit following administration of the first cycle of drugs. If a severe adverse event occurs at any time during administration of the 2-day drug regimen, the study will pause, and a formal review will occur. Subsequent subjects will only be enrolled if the SAE is determined to be unrelated to the study drug. Other interventions will be as according to the direction of the FDA and Mayo IRB.

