### 4.4 Early Withdrawal of Subjects

#### 4.4.1 When and How to Withdraw Subjects

All subjects will be assessed during the 2 days of medication administration, subsequent days of medication administration, and all study visits. If a severe adverse event (SAE) occurs at any time during administration of the 2-day drug regimen, a formal review will occur, and subsequent patients will be enrolled one at a time using the same regimen. If three or more events accrue, the pilot study will be held and either a potential dosing regimen revisited, or discontinuation of the study protocol will occur. Other interventions will be at the direction of the Food and Drug Administration and Mayo Institutional Review Board.

Patients may also wish to withdraw if they perceive that their symptoms of carpal tunnel syndrome are not improving, and they wish additional treatment such as surgery or a steroid injection. If they are tolerating the Fisetin otherwise, we will request that they continue the Fisetin in addition to the other treatments, and such patients will continue to be followed, but will be excluded from the final analysis. We aim to continue enrollment until 40 patients complete the 60-day trial time point without intervening treatment for their CTS.

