## **5.2 Treatment Regimen**

The treatment dosing regimen is based on the preclinical information available about Fisetin along with information about similar clinical drug trials using the alternative senolytic compounds Dasatinib and Quercetin. Participants will be administered Fisetin over a two-day course of treatment twice during the study duration. Each day subjects will receive a target dose of 20 mg/kg of body weight. Therefore, for an adult with a body weight of 75 kg, each day the participant will take 15 of the 100 mg capsules. Dosing should be completed in as short of a time as possible, with a goal of 10 minutes and a maximum time of 60 minutes to complete ingestion of the capsules. Subjects can empty the capsules into room temperature or cold drinks or puddings, such as milk, yoghourt, or apple sauce, if they are unable or unwilling to ingest multiple capsules. The drink or pudding will be consumed within 10 to 60 minutes. By mass spectrometry, we verified that Fisetin is stable under these conditions. Dosing will occur at days 0 and 1 and repeated at days 29 and 30.

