## 6.4 Visit 3A, Day 29 ( $\pm 2$ days)

Blood for safety tests will be collected either in Rochester or at another Mayo Clinic site more convenient to the research subject's home within 5 days prior to the scheduled appt on day 29. These results will be reviewed prior to the third IP dose, to confirm there are no clinically significant changes. On day 29, subjects will return to Mayo Clinic's Clinical Trial Research Unit (CTRU). Subjects will have their vital signs measured and review changes to their medical history and concomitant medications with the CTRU nurse to ensure they continue to meet inclusion/exclusion criteria. Women of child bearing potential will confirm their pregnancy status via a point of care pregnancy test. The study team will administer the hand examination including measurement of pinch and grip strength and record the information into REDCap, record adverse events, and collect the Subject Drug Diary. The subject will fill out hand/wrist pain VAS and hand/wrist interference VAS assessments and the Boston CTS (BCTQ) questionnaire in REDCap. The subject will provide a blood and urine sample for inflammation and senescence markers. Finally, the CTRU nurse will administer the third IP dose and provide the subject with IP for the following day (20 mg/kg/day).

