## 8 Safety and Adverse Events

Safety evaluations will include adverse event (AE) and serious AE (SAE) reporting. Adverse event reporting will be conducted throughout the study for all subjects. The reporting period begins at administration of IP (Day 0) and continues through the post treatment follow-up period, –Day 180). Adverse events will be assessed at Day 0, 29,, 60, and 180. Subjects will be encouraged to contact the Primary Investigator or study coordinator immediately if they experience any AE or SAE's during the study.

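### The single-event pause and formal review apply only on the four dosing days, so a first non-fatal, possibly related SAE between or after the courses triggers neither

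*Combined protocol and SAP*

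**What the plan says.** The rule for a single event appears twice.

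- Section 8.5 (Stopping Rules) says of a severe adverse event that if it "occurs at any time during administration of the 2-day drug regimen, the study will pause, and a formal review will occur". It adds: "Subsequent subjects will only be enrolled if the SAE is determined to be unrelated to the study drug".
- Section 4.4.1: if such an event "occurs at any time during administration of the 2-day drug regimen, a formal review will occur", and then "subsequent patients will be enrolled one at a time using the same regimen".

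Section 8.5 counts administration as four days in all. Section 5.2 places them: "Dosing will occur at days 0 and 1 and repeated at days 29 and 30".

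Adverse events are collected for much longer. Section 8 states: "The reporting period begins at administration of IP (Day 0) and continues through the post treatment follow-up period", that is, to Day 180.

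Two study-level rules work by count. Section 4.4.1 says: "If three or more events accrue, the pilot study will be held". The toxicity stopping rule in section 8.5 ends the study at any treatment-related death or at more than 3 SAEs. There is no formal DSMB (section 8.6.1). The investigator monitors under a safety monitoring plan that is not part of the documents.

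**The concern.** The protocol treats one severe event during a dosing course as reason enough to stop and look before anyone else is exposed. It gives no reason why a related serious event that appears some days after a course should count for less. For a drug given in two short courses a month apart, delayed toxicity would show itself between or after the courses.

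The scheduled safety labs are also timed to find problems outside the dosing days. A serious laboratory toxicity first seen at the Day 29, 45 or 60 draw would not meet the trigger unless its onset were traced back to a dosing day. Other subjects, whether newly enrolled or waiting for their second course, could meanwhile receive the same regimen without a required formal review of that event.

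**Working it through.** **Step 1: length of the window.** Section 8.5 gives 2 cycles × 2 days = 4 days. Section 5.2 lists Days 0, 1, 29 and 30, which is also 4. The figures agree. The second dose of a course may follow the first by 12 to 36 hours (sections 6.3 and 6.5), and Visit 3A has a ±2-day window. Calendar days can therefore shift, but each subject still has four dosing days.

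**Step 2: days covered.**
- Days 0 to 60 inclusive: 61 days. 4/61 = 6.6%, with 61 − 4 = 57 days outside.
- Days 0 to 180 inclusive: 181 days. 4/181 = 2.2%, with 181 − 4 = 177 days outside.

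**Step 3: when scheduled labs could find a problem.** Section 6.9.7 sets safety labs at Days 29, 45 and 60. The Day 29 set may be drawn up to 5 days earlier, and section 6.4 says: "These results will be reviewed prior to the third IP dose". No scheduled post-dose safety lab therefore falls within a dosing course.

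**Step 4: trace one event.** Take a first, non-fatal, possibly related SAE starting on Day 10 in one subject.

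| Provision | What it requires for this event | Study-level pause or event-triggered formal review? |
|---|---|---|
| 4.4.1 and 8.5, single-event rule | Nothing; not during administration | No |
| 8.5, individual stopping | That subject receives no more drug | No |
| 8.1, abnormal laboratory values | Repeat test, call, visit or referral for that subject, if a laboratory change is involved | No |
| 8.2 and 8.3 | Immediate recording and reporting; sponsor-investigator evaluation | No |
| 8.3.1 and 8.3.2 | IRB reporting under policy; FDA report in 7 or 15 calendar days if an unexpected suspected reaction | No |
| 8.5, FDA or IRB direction | Whatever is directed | Only if directed |
| 8.6 | Regular assessment of the number and type of SAEs | Study-level, but not triggered by the event |
| 4.4.1, three-event hold | Not reached at one event | No |
| 8.5, toxicity rule | Not reached at one non-fatal event | No |
| Section 10, to which 8.6 refers | Monitoring and audit access | No trigger stated |

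**Step 5: events needed for the next mandatory study-level action.** Section 4.4.1 does not say whether its three events include those outside the dosing days. If they do, two such SAEs pass and the third brings a hold. If they do not, three pass and the fourth brings termination, because the toxicity rule needs more than 3. As written, the toxicity rule counts SAEs of any timing and cause, so fewer would pass if unrelated SAEs had already been counted.

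**The case against.** The design can be read as deliberately tiered: an acute trigger during dosing, an individual stop at any time, and termination for a related death or accumulated SAEs at any time. Fisetin is marketed as a supplement and given on four days only, and section 1.6 anticipates no serious events. Neither statement of the rule says who conducts the formal review. At a single site with a sponsor-investigator, it may differ little from the evaluation already required. These points lower the weight of the gap. They do not close it, because none makes a pause or formal review follow from the event itself.

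A reader might infer more than the documents support:

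- **That no study-level review is required outside dosing days.** Section 8.6 requires a regular assessment of SAE numbers and types, with no limit to dosing days. What is missing is the automatic response to a single event.
- **That 97.8% of the risk is uncovered (177 of 181 days).** Risk need not be spread evenly over days and may well cluster around dosing.
- **That the chance of harm can be put as a probability.** The documents give no SAE rate. A figure from an assumed rate would also count events after which nobody is left to dose.
- **That other subjects would in fact be dosed without review.** A prudent investigator might pause anyway, the FDA or IRB could direct it, and the monitoring plan might require it.
- **That the trigger should run to Day 180.** A single event up to 150 days after the last dose (180 − 30) is a weak reason for an automatic pause.

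**Conclusion.** The gap is real on the text. Both statements of the single-event rule are tied to administration, and no other provision in the documents makes a first non-fatal, at least possibly related SAE on another day pause the study or start a formal review. The only measure of its extent is 4 of 61 days through Day 60, or 4 of 181 through Day 180. The practical consequence depends on the monitoring plan not containing such a trigger, and that cannot be checked. This is a matter of safety governance and does not touch the efficacy analysis. It is a cheap improvement.

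**What to change.** In sections 4.4.1 and 8.5, keep the dosing-day rule and add:

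> Any serious adverse event (section 8.1) at least possibly related to study drug, with onset from first dose through Day 60 (30 days after the last dose), triggers a short pause in new enrolment and dosing and a formal review while any subject remains to be dosed. Enrolment and dosing resume if the review finds the event unrelated or the risk acceptable.

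Also state that:

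- the last sentence above governs resumption for the added trigger. If the existing clause in 8.5, which allows enrolment only after an unrelated finding, applied here too, a first related event would in effect end the study;
- one-at-a-time enrolment after such an event is for the review to decide;
- the three-event hold in 4.4.1 counts SAEs over the same window;
- a late second course is, or is not, allowed after a pause.

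Use serious, not severe, for the added trigger. Section 8.3.1 grades as severe any problem needing more than one day of over-the-counter medication, which would set the bar too low. Day 60 is a judgement, but section 4.1 already uses 30 days after the last dose for contraception. If the monitoring plan already holds this trigger, citing it in 8.5 is enough.

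The cost is a protocol amendment and an occasional short pause, which may slow accrual or push a second course outside the ±2-day window of Visit 3A.

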### **Premature withdrawal from study:**

Subjects may voluntarily withdraw from the study for any reason at any time. Subjects are considered withdrawn if they state an intention to withdraw further participation in all components of the study, die, or are lost to follow-up for any other reason. The investigator may withdraw a subject from the study (without regard to the subject's consent) if they believe that continued participation in the study would be contrary to the best interests of the patient.

Subjects are considered as lost to follow-up if all reasonable attempts by the investigator to communicate with the individual fail. The investigator will take preventive measures to avoid a subject being lost to follow-up (*e.g.*, document different ways of contact such as telephone number, home address, e-mail address, person to be contacted in case the subject cannot be reached). If the subject cannot be reached, the investigator will make a reasonable effort to contact the subject, document all attempts and enter the loss of follow-up information into the Case Report Form (CRF). The following methods will be used: at least two telephone calls will be placed to the last available telephone number (each call on different days) and one registered letter will be sent by post to the last available home address. If the subject is still unreachable after all contact attempts listed above, he/she will be lost to follow-up.

If premature withdrawal occurs for any reason, the reason for premature withdrawal from the study, along with who made the decision (subject, investigator) will be recorded in the CRF.

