### Toxicity stopping rule

The study will be terminated if the number of **treatment related** deaths exceeds 0 or if SAE's in the subjects already registered and treated in the trial exceeds 3.

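### Sections 4.4.1 and 8.5 conflict on enrolment after a first severe adverse event that is judged related to Fisetin or cannot be classified

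*Combined protocol and SAP*

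**What the plan says.** Two sections of the protocol state what follows a severe adverse event that occurs during a 2-day course.

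- **Section 8.5, Stopping Rules:** "the study will pause, and a formal review will occur". It then sets the condition for restarting: "Subsequent subjects will only be enrolled if the SAE is determined to be unrelated to the study drug".
- **Section 4.4.1, When and How to Withdraw Subjects:** "a formal review will occur, and subsequent patients will be enrolled one at a time using the same regimen". The next step comes later: "If three or more events accrue, the pilot study will be held", after which the dosing is reconsidered or the study is discontinued.

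Both sections leave other interventions to the FDA and the IRB. Under 8.5, the individual rule takes an affected subject off drug. The toxicity rule ends the study on any treatment-related death, or when the count of SAEs "in the subjects already registered and treated in the trial exceeds 3". Section 8.6.1 says there is no formal DSMB and that the principal investigator monitors adverse events.

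**The concern.** The trigger is the same in both sections, but the instructions differ. After a related first event, a reader of 8.5 closes enrolment. A reader of 4.4.1 enrols the next patient at the dose just implicated. Neither section refers to the other or ranks itself above it. A stopping rule has to be settled before it is needed, and here the investigator who monitors events would have two versions to choose from.

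A smaller matter is dosing. Doses 2 and 4 are taken at home; at Visit 3A, for example, staff "provide the subject with IP for the following day". Section 8.5 does not say expressly that its pause reaches doses already dispensed or still due to other subjects.

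**Working it through.** The plan has no figure to reproduce here, so the check is a comparison of the two rules, followed by an illustration of how often the difference could matter.

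**1. The rules side by side**

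| After a first event | Section 8.5 | Section 4.4.1 |
|---|---|---|
| Formal review | Yes | Yes |
| Pause | Yes | Not named |
| Enrolment if unrelated | May resume | Continues singly, same dose |
| Enrolment if related | Barred | Continues singly, same dose |
| Enrolment if undetermined | Barred (not found unrelated) | Continues singly, same dose |
| Hold | From the first event | Named at three or more events |

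The unrelated row can be reconciled by reading the sections in sequence: pause, review, resume singly. The related and undetermined rows cannot.

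**2. Whether other text settles it**

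- The FDA and IRB clauses cover other interventions, not the choice between the sections.
- The individual stopping rule concerns only the affected subject.
- The toxicity rule acts on a treatment-related death or on a fourth SAE (more than 3). It is compatible with a hold at three and does not address a first non-fatal event.

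**3. How often the sections would diverge**

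Inputs: n = 40 enrolled (Study Summary). The per-subject probability p of a related event during dosing is assumed, because the documents give no rate and Section 1.6 anticipates no serious events. Subjects are treated as independent.

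P(at least one) = 1 − (1 − p)^40

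- p = 0.01: 1 − 0.669 = 0.331
- p = 0.02: 1 − 0.446 = 0.554
- p = 0.05: 1 − 0.129 = 0.871

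For comparison, P(at least three) = 1 − Σ C(40, j) p^j (1 − p)^(40−j), summed over j = 0 to 2. This gives 0.007, 0.046 and 0.323. It counts related events only. The hold in 4.4.1 has no relatedness limit, so these values are lower bounds on the chance of reaching it.

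**4. Subjects whose dosing a pause would touch**

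Assume even accrual over 18 months (24 months in all, less 6 months of follow-up; range 12 to 22) and a 14-day review.

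- Accrual rate = 40 / (18 × 30.44) = 0.0730 per day (0.1095 at 12 months, 0.0597 at 22).
- Day 29 falls inside the review: 0.0730 × 14 = 1.02 subjects (1.53 to 0.84).
- The whole Day 27 to 31 window is lost: 0.0730 × (14 − 4) = 0.73 subjects (1.10 to 0.60).
- Holding a take-home dose at any moment: 0.0730 × 1 day × 2 courses = 0.15 subjects (0.22 to 0.12).

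**The case against.** The best defence is that 8.5 carries the title Stopping Rules while 4.4.1 is about withdrawal, so a careful team would follow the stricter section and satisfy most of both. FDA and IRB direction stands behind it, and the lack of a formal DSMB does not leave the investigator acting alone. This lowers the practical risk. It does not remove the conflict, since nothing gives 8.5 precedence.

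Several stronger readings are tempting, and the documents do not support them:

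- *That 4.4.1 lets the study run unreviewed until the third event.* It requires a formal review after the first.
- *That the sections clash for every event.* For an unrelated event they can be followed in order.
- *That other subjects would go on being dosed during a pause.* A study pause naturally covers dosing, and silence in 4.4.1 does not contradict that. The numbers involved are also small.
- *That the conflict is worth a definite number of enrolled subjects.* Counting related events only, expected enrolment at p = 5% is 17.4 if it stops at the first event and 35.9 if it stops at the third, a gap of 18.5. But 4.4.1 counts all events. With unrelated events at an equal assumed rate, 35.9 falls to 26.8 and the gap to about 9.4. The calculation also ignores replacement of withdrawn subjects and treats the 8.5 stop as permanent, so it is not a sound measure.
- *That the trigger must be narrowed to serious events.* Both sections mix severe with SAE, which the abbreviation list gives as serious. The severe grade in 8.3.1 is broad ("any problem requiring more than one day of OTC medication, or requiring a doctor visit"). Narrowing the trigger is nevertheless a separate safety decision.

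**Conclusion.** The safety rule is wrong as written, within a limited scope. For a first event judged related, or not yet classifiable, 8.5 bars further enrolment and 4.4.1 continues it. No other text decides between them. For an unrelated event there is no real conflict.

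The contradiction itself rests on the text alone. Its practical weight depends on an event rate the documents do not give: under the assumed 2% per subject, the chance of reaching the point of divergence is 55%, and over 1% to 5% it runs from 33% to 87%. Replacing withdrawn subjects would put more than 40 on drug and raise these figures somewhat. The primary analysis is not affected. This is a point for the sponsor to consider and correct, and the dosing question is a side note to it.

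**What to change.** Put one rule in both places. Replace the first-event sentence in 4.4.1, and state the same in 8.5, along these lines:

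> The study pauses for the formal review set out in Section 8.5. If the review finds the event unrelated to Fisetin, enrolment restarts singly at the unchanged dose. If the event is found related, or relatedness cannot be determined, enrolment stays closed until the FDA and IRB give direction.

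Keep the three-event hold in 4.4.1 and the termination rule in 8.5.

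Two additions to 8.5 would help. State that the pause covers doses still due to enrolled subjects, including take-home doses. State also whether a dose held beyond its visit window is given late or omitted. A held dose would not by itself make the subject withdrawn, since 4.4.1 reserves that for those who state "an intention to withdraw further participation in all components of the study", die or are lost to follow-up, or whom the investigator withdraws. Take up any change of trigger from severe to serious separately.

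The cost is a few sentences, with no added patients or analyses. Under the accrual assumption above, about one subject per 14-day review could have the second course delayed or missed. A postponed Visit 3A may also need a repeat safety draw, because Section 6.4 requires those labs within 5 days before the visit.
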